#### **TMS Protocol:**

During TMS, a pulsed magnetic field is produced by a small coil positioned over a targeted area on the scalp, inducing an electric current in the brain that temporarily modulates cortical activity. Repetitive TMS (rTMS) paradigms use trains of pulses to induce cortical effects that outlast the duration of stimulation. The direction of the rTMS effect, either facilitation or suppression of cortical activity, depends on pulse frequency and sequence (i.e., intertrain interval). Research using neuroimaging and electrophysiological recordings has demonstrated that single low frequency (1Hz) and continuous bursting frequency (continuous theta burst stimulation; cTBS) induce inhibitory effects. rTMS augmentation of cortical targets can impact local activity, connectivity, and network properties. TBS and conventional rTMS have comparable effects on cortical excitability and similar safety profiles in pediatric samples. TBS has particular advantages for a pediatric population, specifically much shorter stimulation duration (i.e., 2-3 min for TBS vs. 20-30 min for rTMS) and lower stimulation intensity.

**TMS Device.** We will use a Magstim SuperRapid2 Plus 1 TMS system with matching active and sham air-cooled coils (Magstim, Carmarthenshire, UK) (<http://www.magstim.com>, UK) to stimulate over pSMA target.

**TMS Targeting.** Targeting will be carried out using the 10-20 EEG system. Scalp vertex (Cz) will be defined based on the midpoint of the inion and the nasion on the sagittal midline. Prior research has defined the SMA as 15% of

[figure not shown]
[figure not shown]
the distance between inion and nasion (I-N distance) anterior to Cz. Our research using neuronavigation to locate left pSMA indicated that average distance from Cz is 15.9% of the I-N distance anterior to Cz. Based on this information, we will target 16% of the I-N distance anterior to Cz (placement illustrated in the figures below, 1.5 cm from midline).

Category	Parameter
	Coil type
Shape	Figure 8
Size	70mm
	Coil Placement
Orientation	45°
Stimulation site	Left pSMA
Method for locating stimulation site	Scalp measurement based on 10-20 system
	Stimulation parameters
Pulse intensity	90% RMT
Pulse frequency	30 Hz
Train length	40 sec
Number of trains	1
Intertrain interval	0
	Session parameters
Pulses per session	3
Number of sessions	1

**TMS Parameters.** TMS will be delivered over pSMA using cTBS. Research using neuroimaging and electrophysiological recordings has demonstrated that single low frequency (1Hz) and cTBS typically induce inhibitory effects. rTMS augmentation of cortical targets can impact local activity, connectivity, and network properties. TBS and conventional rTMS have comparable effects on cortical excitability and similar safety profiles in pediatric samples. TBS has particular advantages for a pediatric population, specifically much shorter stimulation duration (i.e., 2-3 min for TBS vs. 20-30 min for rTMS) and lower stimulation intensity. cTBS will consist of bursts of 3 pulses at 30 Hz repeated every 200ms (5 Hz burst frequency), single uninterrupted 40 sec train, 600 total pulses; 90% RMT. This sequence has been used in prior pediatric compulsivity samples. 30 Hz is advantageous over conventional 50 Hz TBS in developmental samples as it can be delivered at higher stimulation intensity and children have higher motor thresholds. Single session aftereffects are approximately 60 min for cTBS.

**Motor threshold (MT) determination.** Resting MT will be defined as the minimum magnetic flux needed to elicit observed twitch of the thumb (resting target muscle: abductor pollicis brevis) in 5/10 trials using single-pulse TMS administered to the contralateral hand area of primary motor cortex (as described by Badran and colleagues). The MT procedure will occur during the first visit and this MT will be used to calculate stimulation intensity for all TMS sessions. Patients will be in the same position (upright) during both motor threshold and stimulation procedures. The figure below demonstrates placement for eliciting twitch in resting target muscle (abductor pollicis brevis):

**Sham procedures.** Sham stimulation will use the Magstim sham air-cooled coil, which produces auditory signals identical to an active coil but contains a mu-metal shield that diverts the majority of the magnetic flux such that a minimal (<3%) magnetic field is delivered to the cortex. Forms assessing blinding adequacy will be given to participants, parents, and blinded staff who study visits.

**Masking** procedures will be implemented to control for expectancy effects related to TMS stimulation. Persons who will be masked to TMS status are: participants; parents (if applicable), study staff administering clinical assessments, SST, and EEG, study staff administering TMS, and all study investigators except for the study statistician responsible for randomization. Forms assessing masking adequacy will be given to participants, parents, and staff administering TMS. Study staff administering TMS will remain masked using the following procedures. The Sham and Active Coils are identical in appearance. The motor threshold coil which will be used for all procedures is different in appearance than the active and sham treatment coils. Each coil will each be labeled with a unique random number (e.g. 1639 vs 2740) but the technician will not know which is active and which is sham. The Neuromodulation Facility Manager will hold the masking log in a secure location. A masked TMS coil assignment log (included in CRF) will be used for the study with consecutively consented subjects assigned to consecutive ID#s that appear in the form. For each ID# there will be a coil number (e.g., 1639 or 2730) assigned in random order prior to start of the study. At the time of each treatment, the technician will confirm the participant's name and consult this form to select the correct coil to attach for the treatment session that day. The date of each session must be documented, along with the maximum intensity (relative to MT) applied in the session that day,etc.

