#### Study Design Flow Chart:

#### Study Assessment Measures:

- 1) Mini-Kid; the Mini-Kid 7.0 is a brief, structured interview measuring psychiatric diagnoses in children according to DSM-V and ICD-10 criteria.
- 2) CY-BOCS, is the “gold standard” clinical interview for assessment of OCD symptoms.
- 3) Screening Questionnaire for TMS Candidates; screens for TMS contraindications and will be administered in an interview format with both the child and parent present.
- 4) TMS Adverse Effects Questionnaire (AEQ) is a 13-item questionnaire completed by patient (items 1-10) and clinician (items 11-13).
- 5) The SST is a well-validated computerized task measuring RI. The SST is a visual choice reaction time task in which participants watch arrows (left or right) on the screen and respond by pressing the appropriate button. In a randomly assigned proportion of trials, an audible signal is heard after presentation of the arrow, and subjects are instructed to inhibit the motor response (button press). The inter-stimulus interval and stop-signal delay are varied according to individual performance so that each person can successfully inhibit responses to 50% of stop trials. SSRT (time required to inhibit a prepotent motor response) is calculated from these data. Successful stop trials (i.e., those in which a motor response is successfully inhibited) are most relevant for understanding functional neural correlates of RI, and will be of primary interest in EEG analyses (see below).
- 6) EMA will be used to obtain youth ratings on three items (modified from NIMH rating scales) assessing obsessions, compulsions, and mood on a 7-point scale (1 = not at all to 7 = very much). These items have shown differential change with frequent assessment post-TMS for adults with OCD and have been used in EMA studies of OCD. Youth will receive a text message prompt every two hours (between 9am and 9pm) over the two days following the clinical interview and each study visit (6 days total). The text prompt will include a redcap link for completing EMA items. Similar EMA items and procedures have been used successfully with adolescents of diverse backgrounds in a large number of studies to date.

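### No re-coding of the two treatment coils is described, so one correct inference by the technician would reveal the allocation of every later session

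*Combined protocol and SAP*

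**What the plan says.** All of this is in the combined protocol and SAP. The Masking paragraph lists the staff who deliver TMS among those kept unaware of allocation and says: "Study staff administering TMS will remain masked using the following procedures". The procedures are:

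- Appearance: "The Sham and Active Coils are identical in appearance".
- Labels: "Each coil will each be labeled with a unique random number (e.g. 1639 vs 2740) but the technician will not know which is active".
- Assignment: "For each ID# there will be a coil number (e.g., 1639 or 2730) assigned in random order prior to start of the study". The log lists consecutive IDs.
- Use: at each treatment the technician is to "consult this form to select the correct coil to attach for the treatment session that day".
- Key: the Neuromodulation Facility Manager keeps the masking log in a secure place.
- Check: participants, parents and TMS staff complete forms on masking adequacy.

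Under Sham procedures, the sham coil "produces auditory signals identical to an active coil but contains a mu-metal shield that diverts the majority of the magnetic flux", leaving less than 3% of the field to reach the cortex. Scalp sensation and muscle twitch are not mentioned.

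The design is a two-visit crossover in 14 youths, each receiving one active and one sham session. Nowhere are the coil numbers re-issued, rotated or covered. Nor does the text call them permanent; that reading follows from one number per coil, a log completed in advance and no later step.

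**The concern.** A coil code protects the operator only while it carries no information from one session to the next. With two codes serving the whole trial, the technician sees the same two numbers repeatedly beside whatever can be seen or heard in the room. Once one number is correctly linked to active or sham, the other follows by elimination. The log then shows the allocation of all later sessions, including the treatment order of participants not yet seen.

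The plan gives masking as its control for expectancy and deliberately extends it to TMS staff. The likely exposure is in cues to the youth, given before the post-stimulation stop-signal task and before the EMA ratings of the following two days. Items 11-13 of the Adverse Effects Questionnaire (AEQ), which a clinician completes, are also exposed if the technician is that clinician.

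**Working it through.** The plan gives no figure to reproduce here. The check is a reading of the procedure followed by an illustration.

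**1. Codes and sessions.** 14 participants × 2 visits = 28 planned sessions. Two coils with one number each give two codes. If the first session were revealing, the other 27 would be known.

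**2. What each safeguard does.**

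- Identical appearance and identical sound make a revealing session less likely. They do not limit what follows from one.
- The secured key stops the technician looking up the answer. It does not stop the technician inferring it.
- The masking forms measure whether masking held. They do not preserve it.

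None of these confines a break to the session or participant where it occurs.

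**3. Illustration.** Assumptions, none from the documents: each participant's one active session reveals its coil with probability p; sessions are independent; participants are treated in sequence; one technician treats all 14.

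- Probability that the code is broken by participant k: 1 − (1−p)^k.
- Expected share of participants whose technician knows the allocation, counting the participant whose session breaks the code: the mean over i = 1 to 14 of 1 − (1−p)^i, which equals 1 − [(1−p)(1 − (1−p)^14)/p]/14.
- With single-use codes a revealing session exposes only that participant, so the share is p.

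For p = 0.05: 0.95 × (1 − 0.4877)/0.05 = 9.73; 9.73/14 = 0.695; share = 0.305.

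| p per active session | Broken by participant 5 | Broken by participant 14 | Share, two fixed codes | Share, single-use codes |
|---|---|---|---|---|
| 0.05 | 23% | 51% | 30% | 5% |
| 0.1 | 41% | 77% | 50% | 10% |
| 0.2 | 67% | 96% | 73% | 20% |

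Both share columns count the revealing participant, so they are comparable. Counting only participants treated after the break (mean of 1 − (1−p)^(i−1)) lowers the fixed-code shares to 27%, 45% and 66%.

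**4. Sensitivity.**

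- Two technicians treating seven participants each, without sharing guesses: replacing 14 by 7 in the share formula gives 18%, 33% and 55% (for p = 0.05: 0.95 × (1 − 0.6983)/0.05 = 5.73; 5.73/7 = 0.819; share = 0.181).
- Either type of session may reveal, p = 0.05 per session: expected sessions with an unmasked technician under two fixed codes are the sum over k = 1 to 28 of 1 − 0.95^k = 13.5. If a break is confined to the participant, the figure is 14 × (0.05 + 1 − 0.95²) = 2.1. The participant is the right unit for that comparison because, in a two-period crossover, knowing visit 1 gives away visit 2 even under fresh codes.
- Extremes: if a cue shows in nearly every active session, the technician recognises the coil whatever its label. If it almost never shows, neither scheme is broken. Re-coding matters between these limits.

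**The case against.** The strongest reply is that the leak itself is not documented. A reader might infer from the mu-metal shield that the coils certainly feel different or produce a different visible twitch. The documents support only a difference in field reaching the cortex; the step to something the operator can notice is plausible but unproven. That stands, and it is why p is shown as an assumed range and the percentages are not forecasts for this trial.

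Second, the codes are never said to be permanent. The example numbers differ between two sentences (1639 and 2740, then 1639 and 2730), and the log is said to hold one coil number per ID although a crossover needs one per visit. A reader might take the differing examples as a sign of changing codes. A slip is likelier, since 1639 appears in both, but the wording should be reconciled.

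Third, a reader might infer that a technician who has broken the code would bias the main outcomes. The documents do not show this. Staff running clinical assessments, the stop-signal task and EEG are listed separately from TMS staff, though not stated to be different people. Nothing says the technician coaches the task, inspects EEG or rates the AEQ. SSRT comes from a computerized task, ten of the 13 AEQ items are the patient's, and EMA is self-rated. A break also cannot change how completed sessions were conducted, even if the log lets the technician decode them afterwards.

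Fourth, the illustration depends on one technician and independent sessions, and the gap narrows when either is relaxed. That is correct, as the sensitivity figures show.

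These points limit the size of the concern. None supplies a step that stops one correct inference from carrying forward.

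**Conclusion.** The point holds as a weakness in how the masking scheme contains a break. As written, two codes serve 28 sessions, the technician sees the code at each one, and a single correct inference opens the rest of the log. Under the stated assumptions, about 30%, 50% or 73% of participants would have a technician who knows the allocation, against 5%, 10% or 20% with single-use codes. The contrast is more informative than either level, because p cannot be drawn from the documents.

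It would go too far to say that operator masking will fail, or that the trial does not merit the term double-blinded. Sensible safeguards against a first break are in place, and the route from an unmasked technician to the outcomes is only partly established. The change is worth making because it is cheap and leaves stimulation, schedule, sample size and analysis untouched.

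**What to change.** Amend the Masking paragraph as follows.

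- Replace the two standing coil numbers with session-specific codes, two per participant and 28 in all, and state how both visits are listed for each ID.
- Before each session the Facility Manager, who already holds the masking log, covers the coil label and serial plate with that session's code.
- Give the technician only that session's code, not the log of other IDs.
- Have the manager check the coil's serial number against the key and record it before each session. A check only at database lock would find a wrong-coil error after the session had been delivered.
- State that the manager is unmasked (the Randomization section exempts only the statistician) and should have no other contact with the participant or the ratings.
- State whether the technician may complete AEQ items 11-13, and correct the mismatched example numbers.

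The cost is revised wording, 28 labels and a few minutes of handling per session. There is a small risk of mislabelling, which the pre-session check limits, and the key holder comes closer to the sessions. The change contains the spread of operator unmasking. It does not remove any sensory cue, and it does nothing for participants, who experience both coils; the masking forms remain necessary for that.

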#### Description of the Statistical Methods:

Statistical methods align with the Aims of the study, which are as follows:

**Aim 1. Safety and Tolerability.** TMS will be safe and tolerable, as indicated by a comparable rate of side effects associated with TMS vs. Sham (hypothesis 1) and no serious adverse events associated with TMS (hypothesis 2).

**Aim 2. Neural Target Engagement: TMS-induced changes in the RI Network.** Compared with sham, participants will demonstrate significant post-TMS neural changes during SST stop trials, as indicated by increase in frontocentral P3 amplitude

**Aim 3. Behavioral Target Engagement: TMS-induced changes in RI behavior.** Compared with sham, participants will demonstrate a significant post-TMS decrease in SSRT (Hypothesis 1) and EMA-rated compulsions (Hypothesis 2).

**Data Analysis.** We will test **Aim 1 (Safety and Tolerability)** using descriptive data as follows. Hypothesis 1. TMS will be safe and tolerable as shown by total AEQ ratings that are no more than 1 SD higher for TMS vs. Sham (hypothesis 1) and no serious adverse events associated with TMS reported on the AEQ (hypothesis 2). Remaining analyses will use Generalized Linear Mixed Models (GLMM), a variant of Generalized Linear Models (GLM; of which ANOVA, t-test, and regression are special cases) that permit outcome variables with distributions other than Gaussian and additionally permit modeling both fixed and random hierarchical (nested) effects. For each model, the distribution will be selected based on theory (e.g., Poisson for count) and model residuals. **Aim 2 (Neural Target Engagement).** We will examine the significance of TMS-induced neural changes during SST stop trials by testing an interaction between visit type (TMS vs. Sham) and timing of assessment (pre vs. post TMS/Sham) for the the outcome of frontocentral P3 (hypothesis 1). **Aim 3. Behavioral Target Engagement:** We will test an interaction between visit type (TMS vs. Sham) and timing of assessment (pre vs. post TMS/Sham) on RI efficiency as measured by the SSRT (hypothesis 1) and EMA-rated compulsions (hypothesis 2).

**Sample size and power.** We anticipate some minimal EEG/SST data loss and participant attrition, very conservatively resulting in a final sample size of  $N = 10$  participants (each with four EEG/SST observations; pre- and post- TMS and Sham). Given this sample size and assuming .80 correlation among repeated measures, power calculations indicate that **Aim 2 and 3** analyses would reach 0.8 power with a medium effect size (Cohen's  $d = 0.51$ ) and alpha = .05. Assuming .60 correlation among repeated measures, analyses would reach .8 power with a medium-large effect size ( $d = .70$ ). Using a TMS protocol similar to that proposed in this application, Obseso (2017) found large effect sizes for cTBS of pSMA on SSRT in healthy adults ( $d = .95$ ). Available data for proposed outcome variables suggest that repeated measures correlations will fall between .60 and .80, with SSRT showing correlations between .65-.73 and P3 showing correlations of .68-.71.

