**Participants:**

The participants for this study will consist of 14 youth ages 13-18 years with OCD.

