**Study Design:**

We will use a within-subject, counterbalanced design comparing TMS vs Sham in a brief 2-visit protocol enrolling 14 youth (age 13-18) with OCD. At each visit, youth will complete the Stop Signal Task (SST) with concurrent electroencephalogram (EEG) pre- and post- TMS or Sham. TMS will be delivered over pSMA using continuous TBS (cTBS). After each visit, youth will rate symptoms using ecological momentary assessment (EMA).

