**Study Procedures:**

Overall, study procedures include (a) pre-screening for initial eligibility determination; (b) clinical interview for final eligibility determination, (c) two study visits at which youth will receive TMS or Sham and complete EEG and SST procedures. Assessment procedures include structured diagnostic interviews, and safety screening for TMS. Interested participants will complete a brief phone screen and provide medical records for review before scheduling a clinical interview. Clinical Interview: Participants will complete informed consent (signature required from one parent/guardian), child assent, and assessment of inclusion/exclusion criteria (Mini Kid, CYBOCS, TMS screen; see Measures). Interviews will be administered by the RA, who is already employed at PARC and trained to a reliable standard on all measures. At each of visits 1 and 2, participants will complete a TMS safety screen and medication tracking form; they will then complete the SST with concurrent EEG pre- and post- TMS or Sham. The AEQ will be completed at the end of each visit. Between visits, youth will rate symptoms using EMA (see Measures). Visits 1 and 2 will occur at least one week apart to ensure that any acute TMS effects are no longer active by visit 2. Single session rTMS aftereffects on EEG suggests aftereffect durations <70 min.

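### Aim 1 treats zero TMS-associated SAEs, together with comparable AEQ totals, as showing safety, but no upper bound is planned; 0 of 14 would still leave per-participant risks up to 19.3% unexcluded

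*Combined protocol and SAP*

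**What the plan says.** Under Description of the Statistical Methods, Aim 1 predicts that TMS will be safe and tolerable and names two indicators: a comparable side-effect rate and "no serious adverse events associated with TMS (hypothesis 2"). The Data Analysis paragraph in the same section makes both operational. The first criterion is "total AEQ ratings that are no more than 1 SD higher for TMS vs. Sham (hypothesis 1"), and the second is "no serious adverse events associated with TMS reported on the AEQ (hypothesis 2"). Aim 1 is to be tested "using descriptive data as follows".

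The exposure is small. Study Design describes a "within-subject, counterbalanced design comparing TMS vs Sham in a brief 2-visit protocol enrolling 14 youth (age 13-18) with OCD", so each participant has one active visit and one sham visit. The Participants section gives the same total: "The participants for this study will consist of 14 youth ages 13-18 years with OCD".

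The Sample size and power paragraph covers Aims 2 and 3 only. It expects EEG/SST data loss and attrition, "very conservatively resulting in a final sample size of" 10. Nowhere does the plan give an acceptable SAE rate, a confidence limit or an error rate for Aim 1.

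**The concern.** Hypothesis 2 turns an observed count of zero into part of a conclusion about safety. With so few exposures, zero is a likely result even when the underlying risk is not small, so the count needs an upper bound to show what it excludes. The plan provides none.

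If the plan is followed as written, a report could state that TMS was shown to be safe in adolescents when the data exclude only quite high SAE risks. The issue is the strength of the conclusion. It would remain even if every SAE were captured perfectly, and it is separate from how the 1-SD comparison of AEQ totals is defined.

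**Working it through.** **Plan's own figure.** There is none to reproduce. The stated power figures concern Aims 2 and 3 and have no bearing on an SAE count.

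**Inputs from the documents.** Planned exposure is n = 14 with one active session each (Participants; Study Design). The smallest sample mentioned is n = 10 (Sample size and power).

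**Assumptions.** Participants are independent, and all TMS-associated SAEs are captured. The true risks used in step 2 are illustrative, because the documents give none.

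**Step 1: what zero events exclude.** With 0 of n, the exact (Clopper-Pearson) one-sided 95% upper bound solves (1 − p)^n = 0.05, so p = 1 − 0.05^(1/n).

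- n = 14: 1 − 0.05^(1/14) = 19.3%
- n = 10: 1 − 0.05^(1/10) = 25.9%

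This step uses no assumed risk.

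**Step 2: how often hypothesis 2 is met.** P(no SAE) = (1 − p)^n.

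| Assumed true risk | n = 14 | n = 10 |
|---|---|---|
| 1% | 86.9% | 90.4% |
| 2% | 75.4% | 81.7% |
| 5% | 48.8% | 59.9% |
| 10% | 22.9% | 34.9% |
| 20% | 4.4% | 10.7% |

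**Step 3: the joint rule.** The conclusion also needs hypothesis 1, and the probability that both criteria are met cannot exceed the probability that one is. The step 2 figures are therefore ceilings.

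To see how far below the ceiling the joint rule lies, read hypothesis 1 as a difference in mean AEQ totals of at most 1 SD. Use a normal approximation with the SD treated as known. With true difference δ (in SD units) and within-person correlation ρ, P(hypothesis 1 met) = Φ((1 − δ)/√(2(1 − ρ)/n)). Multiply by P(no SAE), taking the two criteria as independent. At n = 14 and an assumed 5% risk:

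- δ = 0, ρ = 0: 0.9959 × 0.4877 = 48.6%
- δ = 0, ρ = 0.8: 1.000 × 0.4877 = 48.8%
- δ = 0.5, ρ = 0: 0.9071 × 0.4877 = 44.2%
- δ = 0.5, ρ = 0.8: 0.9985 × 0.4877 = 48.7%

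The AEQ criterion lowers the figures little in these cases.

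**Step 4: context.** For zero events to exclude a risk p with one-sided 95% confidence, n must be at least ln 0.05 / ln(1 − p). That is 58.4, so 59 exposed participants, for p = 5%, and 28.4, so 29, for p = 10%.

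**The case against.** The strongest reply is that Aim 1 is expressly descriptive, that safe and tolerable is worded as a hypothesis, and that no go/no-go or stopping decision depends on it. A 14-person study is necessarily insensitive to low risks, and any reader can derive the bound from 0 of 14. It is true that no decision is attached, and that limits the weight of the point. The descriptive label does not remove it, because the same text says the results would show TMS to be safe. A descriptive count supports only the statement that no SAE was observed.

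A reader might also infer several stronger things that the documents do not support.

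- **That a 5% SAE risk would be declared safe 49% to 60% of the time.** The conclusion needs both criteria, so such figures are ceilings. The 5% is an outside assumption. The 60% end rests on n = 10.
- **That only 10 may be exposed.** The figure of 10 is the EEG/SST analysis set. A youth with unusable EEG has still been exposed, and so has one who received active TMS first and then left. Ten exposed would require all four losses to come before active stimulation, so it is a worst case.
- **That the criterion cannot tell safe from unsafe.** At n = 14 it fails about 77% of the time at a 10% risk and about 96% at 20%. It is weak at low risks, not uninformative.
- **That the trial is too small and should be enlarged.** The numbers in step 4 show what a zero count can exclude. The plan sets no risk that this trial must exclude.

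**Conclusion.** The point holds as a mismatch between conclusion and evidence. With zero TMS-associated SAEs in the planned 14, per-participant risks up to 19.3% remain compatible with the data at one-sided 95% confidence; in the worst case of 10 exposed, the figure is 25.9%. The plan would nevertheless count that result, with the AEQ criterion, as showing that TMS is safe and tolerable.

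The bound assumes independent participants, one active session each and full SAE capture. The last is favourable to the plan: "The AEQ will be completed at the end of each visit", so an event arising later might not be counted, which would make a zero count easier to obtain. The pass probabilities in step 2 also depend on illustrative risks and apply to hypothesis 2 alone.

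Nothing here suggests that TMS is unsafe, and nothing in the documents defines what SAE risk would be acceptable. This is a cheap improvement to the plan.

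**What to change.** For hypothesis 2, state that the number of participants with a TMS-associated SAE will be reported over the number actually exposed to active TMS, with the exact (Clopper-Pearson) one-sided 95% upper bound. The bound must be computed for the actual number exposed and not fixed in advance; 19.3% applies only to 0 of 14.

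State that a zero count will be reported as no TMS-associated SAE observed, as a preliminary finding, and will not be described as showing that TMS is safe. Amend the Aim 1 and Data Analysis wording to match. Leave hypothesis 1 in place as the separate tolerability comparison.

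The cost is a few sentences and one binomial limit. No added data, visits or participants are needed, and clinical management is unchanged. The only downside is a less favourable safety statement.

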**7). HARM Form.** At visits 1 and 2, we will administer the HARM form to assess for new or worsening suicidal or homicidal ideation (SI or HI). The Harm Form was developed for SI/HI monitoring by the Child and Adolescent Multimodal treatment Study (CAMS) team^105 and NIMH program staff and was also used in the POTS II and POTS Jr trials for youth with OCD. The form is designed to ascertain the presence of any thoughts, wishes, or behaviors related to self-harm or harm to others since the last study contact. This brief measure consists of two broad initial probes—one asking about self-harm and the other about harm to others—and 5-8 contingent follow-up questions assessing acute risk status.

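### Aim 1 judges safety from the AEQ alone; the HARM form and the EMA mood item have no prespecified summary by condition, so the safety conclusion cannot depend on them

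*Combined protocol and SAP*

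**What the plan says.** The Data Analysis paragraph under Description of the Statistical Methods tests Aim 1 descriptively, on two criteria. The first is "TMS will be safe and tolerable as shown by total AEQ ratings that are no more than 1 SD higher for TMS vs. Sham". The second is "no serious adverse events associated with TMS reported on the AEQ (hypothesis 2"). On timing, Study Procedures says "The AEQ will be completed at the end of each visit".

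Study Assessment Measures describes two further sources that bear on psychiatric state.

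- **HARM form (item 7 of that list):** "At visits 1 and 2, we will administer the HARM form to assess for new or worsening suicidal or homicidal ideation (SI or HI"). It asks about "thoughts, wishes, or behaviors related to self-harm or harm to others since the last study contact".
- **EMA:** three items, "assessing obsessions, compulsions, and mood on a 7-point scale (1 = not at all to 7 = very much"), collected "over the two days following the clinical interview and each study visit (6 days total").

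The rest of the analysis text covers P3 (Aim 2), then SSRT and EMA-rated compulsions (Aim 3). It mentions neither the HARM form nor EMA mood.

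**The concern.** The trial stimulates adolescents with OCD and includes a form whose purpose is to pick up new or worsening ideation. Active suicidality is an exclusion criterion, so a positive answer later on is more likely to be new. The rule that decides safety makes no use of that form. New ideation that is not serious by the trial's reckoning, or lower mood after TMS than after Sham, can appear in the trial's own data and leave both Aim 1 criteria met. The crossover adds an attribution problem: what emerges in the days after visit 1 is first asked about at visit 2, when the participant is under the other condition.

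**Working it through.** The plan gives no figure to reproduce here. The check matches each measure to the analysis text, then works out what the proposed tables could show.

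**1. Measures against analyses**

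| Measure | Collected | Analysed under |
|---|---|---|
| AEQ total; serious adverse events on the AEQ | End of each visit | Aim 1 |
| P3 on successful stop trials | Before and after stimulation, each visit | Aim 2 |
| SSRT | Before and after stimulation, each visit | Aim 3, hypothesis 1 |
| EMA compulsions | Two days after interview and each visit | Aim 3, hypothesis 2 |
| EMA mood | Same prompts | None |
| EMA obsessions | Same prompts | None |
| HARM form | Visits 1 and 2 | None |

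**2. What each source can see, by order.** This reads the last study contact as the previous visit; the plan does not define the term.

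- *TMS at visit 1.* The visit 1 AEQ closes before the following days begin. The visit 2 HARM form looks back over those days. If a finding is also written on the visit 2 AEQ, it belongs to the Sham visit. Raising one participant's Sham total by x points lowers the mean TMS-minus-Sham difference by x/14, which makes the first criterion easier to meet.
- *TMS at visit 2.* No HARM form follows visit 2, so none covers the days after TMS.
- *Either order.* EMA mood is rated for two days after both conditions.

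With 14 enrolled and an even split (assumed), 14/2 = 7 participants fall in each order.

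**3. Precision of a HARM count.** With no positive participants, the exact two-sided 95% upper limit is 1 − 0.025^(1/n):

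- n = 7 (TMS-first only): 1 − 0.025^(1/7) = 41.0%
- n = 10: 30.8%
- n = 14: 23.2%

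Only the n = 7 figure applies to HARM after TMS; the others show the limit if the whole sample were covered.

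**4. Precision of a mood contrast.** Prompts every two hours from 9am to 9pm give 7 a day if both ends are used, so 7 × 2 = 14 per post-visit block. If one end is left out, the count is 6 × 2 = 12. The 95% half-width of a paired mean, in SDs of the paired differences, is t(0.975, n − 1)/√n:

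- N = 14: 2.160/√14 = 0.577
- N = 10 (the plan's expected final sample): 2.262/√10 = 0.715

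The documents do not give that SD, so these widths cannot be turned into scale points.

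**The case against.** A reader might infer three stronger things, and the documents support none of them.

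- *That these findings will go unreported.* Nothing says so. The HARM form is presented as individual monitoring, with follow-up questions on acute risk. What is missing is a prespecified summary and any place in the safety conclusion.
- *That the AEQ could never capture such an event.* The visit 2 AEQ comes after the days in question for TMS-first youth, and a clinician completes items 11–13. The AEQ items are not listed, so a mood item is possible. What stands is that each AEQ is tied to the visit at which it is completed, so an entry at visit 2 counts for the wrong condition in this order.
- *That EMA mood is a safety endpoint the plan forgot.* The plan presents it as a symptom rating, gives it no safety role and does not state which direction is worse. This is why it should not become a pass/fail condition.

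Two further points deserve weight. The statement of Aim 1 refers to serious adverse events without naming a source; only the Data Analysis sentence confines them to the AEQ. That softens the second criterion but still leaves out non-serious ideation and mood. The plan also puts single-session aftereffects at about an hour (under 70 minutes on EEG), so a two-day mood average may seem too late to matter. Yet Aim 3 tests compulsions from the same EMA prompts as an effect of TMS, so the plan does not itself treat that window as uninformative.

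Finally, the order of the HARM form and stimulation within a visit is not stated, so visit 1 HARM cannot simply be assumed to be a baseline.

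**Conclusion.** The point holds as a gap in a stated decision rule. Followed exactly, Aim 1 can conclude that TMS is safe and tolerable regardless of the HARM and EMA mood results, except where an event is also a TMS-associated serious adverse event recorded on the AEQ or is reflected in AEQ items that the documents do not list. In the TMS-first order, about 7 of 14 participants, late recording on the AEQ falls on the Sham side. In the TMS-second order, also about 7 of 14, no HARM form covers the days after TMS, and no change to the analysis can repair that.

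The conclusion assumes an even split of orders and a HARM look-back that reaches to the previous visit. It makes no claim about how often ideation or low mood will occur. At 10 to 14 participants the added results would be descriptive: even no positives among 7 is compatible with a rate of up to 41.0%. This should be corrected, but it does not undermine Aims 2 and 3.

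**What to change.** Add to the Aim 1 analysis:

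1. A listing and count of participants with new or worsening suicidal or homicidal ideation on the visit 2 HARM form, by the condition received at visit 1. Count these in the safety conclusion whether or not they appear on the AEQ, and attribute them to the preceding stimulation. Use visit 1 HARM as the reference only if it is confirmed to be given before stimulation.
2. The within-person TMS-minus-Sham difference in mean post-visit EMA mood, with a 95% CI and the scoring direction stated. Present it as supportive description, with no pass/fail threshold.
3. A stated limitation that no HARM form covers the days after visit 2, so HARM says nothing about those days for participants who receive TMS second.

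The cost is SAP wording and two small tables from data already collected. The safety conclusion becomes slightly harder to reach. No formal comparison of HARM findings between about 7 and 7 participants should be attempted.
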